6.1.2.1 End-of-Treatment Visit

The date of end-of-treatment (EOT) visit will be the decision making date for discontinuing the study treatment by investigators. EOT visit should be the EOT date + 7 days. The items to be completed at the EOT visit are listed in the table below:

Table 5 Procedure	s in the	End-of-Treatment	Visit
--------------------------	----------	------------------	-------

Items	Observation items		
Study Management Procedures			
Prior medications and concomitant medications	Concomitant medications are documented		
Clinical Procedures and Assessments			
Adverse events	Adverse events are recorded		
Electrocardiogram (ECG)	ECG is performed		
Height, weight, and vital signs	Height, weight, and vital signs are measured		
Physical examination and ECOG performance status	Systemic physical examination and ECOG performance status evaluation is performed		
Laboratory Procedures/Assessments (at site)			
Pregnancy test	Blood human chorionic gonadotrophin test is performed as a pregnancy test		

Items	Observation items		
Hematology, serum chemistry, urinalysis	Hematology, serum chemistry, and urinalysis tests are performed		
Thyroid function tests	Thyroid function tests are performed		
Laboratory Procedures/Assessments (by central laboratory)			
ADA	Blood sample for ADA test is collected		
РК	Blood sample for PK test is collected		

6.1.3 Follow-up Period

6.1.3.1 Safety Follow-up

Safety follow-up period refers to the 90 days after the last dose of the investigational treatment or the start of new anti-cancer treatment, whichever occurs earlier. The safety follow-up visit is at 30 days (\pm 3 days) after the last investigational treatment, which has the same items as the EOT visit (refer to Section 6.1.2.1). If the EOT visit occurs in the time window of safety follow-up visit, the same tests and examinations do not need to be repeated. It is recommended to complete all protocol required follow-up evaluations for the safety follow-up at $60\pm$ 3 days and $90\pm$ 3 days after the last dose, or AEs and concomitant medications can be collected through phone call. Concomitant medications are recorded until 90 days after the last dose or the start of new anti-cancer treatment, whichever occurs earlier.

6.1.3.2 Radiology Follow-up

Apart from subjects who discontinue treatment due to radiological disease progression, tumor assessment should be performed at pre-specified regular time points if possible until radiological disease progression, the start of new anti-cancer treatment, death, or the end of this trial, whichever occurs first; follow up with subsequent anti-cancer treatment.

6.1.3.3 Survival Follow-up

Survival status and the following anti-cancer treatment will be assessed every 12 weeks by telephone after the last dose of investigational product.

6.1.4 Unplanned Visit

If an additional follow-up visit is needed, all procedures (including laboratory test results) taken by the investigator should be recorded in the source medical record and unplanned visit page in the eCRF.

6.2 SAFETY ASSESSMENTS

Vital signs, physical examinations, ECOG performance status, laboratory tests, frequency, and severity of AEs and SAEs will be evaluated for safety assessment.

AEs are coded according to PT and SOC in ICH MedDRA.

The safety of investigational products will be assessed according to CTCAE v4.03.

6.2.1 Vital signs

Vital signs include temperature, blood pressure, pulse, and respiratory rate. Additional vital sign monitoring will be performed at the discretion of the investigator according to standard practice or as clinically indicated.

6.2.2 Physical Examination and ECOG Performance Status

Physical examination includes height, weight, overall physical examination, and lymphomaspecific examination. Abnormal changes in the physical examination will be assessed by the investigator. Changes of clinical significance (CS) should be reported as AEs by the investigator.

6.2.3 Electrocardiogram (ECG)

An electrocardiograph will be used to record the 12-lead ECG. ECGs must be recorded after 5 minutes of rest in the supine position. ECG parameters including heart rate, PR interval, QRS interval, QT interval, QTc interval, QRS wave, and T wave evaluation, and investigator's evaluation on ECG should be recorded. Clinically significant ECG findings should be reported as AEs by the investigator.

6.2.4 Laboratory Tests

Blood and urine samples for laboratory tests will be collected as per this protocol.

Tests	Items
Pregnancy test	Blood human chorionic gonadotrophin pregnancy test Urinary human chorionic gonadotrophin pregnancy test (as clinically indicated)
Hematology	Complete blood count (CBC) and hemoglobin
Serum chemistry	Blood urea/urea nitrogen, creatinine, sodium, potassium, magnesium, chloride, calcium, phosphate, glucose, total bilirubin, direct bilirubin, ALT, AST, alkaline phosphatase, lactate dehydrogenase, total cholesterol, total protein, and albumin
Urinalysis	Specific gravity, pH, glucose, protein, cast, ketones, and blood cells
Coagulation	PT, APTT, and INR
HBV, HCV, and HIV	Anti-HIV antibody, HBsAg, anti-HCV antibody, HBV DNA test (only for HBsAg positive subjects), HCV RNA test (only for anti-HCV antibody positive subjects)
Thyroid function	FT3, FT4, and TSH
EBV DNA	EBV DNA

Table 6 Laboratory tests

For clinical laboratory test findings with unknown cause or unexpected results, if clinically significant judged by the investigator, the tests are recommended to be retaken in 24 hours and followed up until test results return to normal range and/or cause found. Clinically significant ECG findings should be reported as AEs by the investigator.

6.3 PATHOLOGICAL ASSESSMENTS

Stained tumor tissue sections and corresponding pathological reports or unstained tumor tissue sections (or tissue block) must be collected at screening for central pathology review. Both fresh and archival biopsies are accepted and can be used by central pathology.

Investigators may enroll subjects before obtaining the result of central pathology review. For subjects whose diagnosis is not ENKTL per central pathology laboratory's judgment, investigators in consultation with sponsor medical monitors will determine whether to continue or discontinue the subject from treatment. See *Central Pathology Manual* for detailed instructions.

In the screening and treatment periods, lesion biopsy may be performed at the discretion of the investigator for pathological examination to confirm radiological findings.

6.4 EFFICACY ASSESSMENTS

Efficacy evaluation will be performed by investigators and IRRC based on Lugano 2014 classification.

Contrast-enhanced CT will be performed at screening and every 12 weeks after the first dose of investigational product. Examined sites include head and neck region (that must include nasal cavity, palatum durum, anterior cranial fossa, and nasopharynx), chest, abdomen, and pelvis. For patients allergic to CT contrast media, enhanced MRI will be used as an alternative. Systemic PET/CT examination will be performed at screening, Week 12, and Week 24. Only enhanced CT will be used for follow-up after first radiological CR or Week 24, whichever comes first. For patients without any measurable lesion, follow-up with PET/CT will be performed until radiological confirmation of CR or progression if the patient hasn't reached CR in the first 24 weeks. Additional PET/CT will be performed if follow-up enhanced CT reveals residual lesion or suspected progression.

If contrast media for CT can be injected when PET/CT is performed and meet requirements for PET/CT and contrasted CT, additional enhanced CT can be skipped. See *Radiology Manual for Study Sites* for details.

Apart from subjects who discontinue treatment due to radiological disease progression, tumor assessment should be performed at pre-specified regular time points until radiological disease progression, the start of new anti-cancer treatment, death, or the end of this trial, whichever occurs first.

Bone marrow aspiration and biopsy should be performed at screening. Subjects with positive bone marrow aspiration/biopsy result or indeterminate overall bone marrow assessment at screening will undergo bone marrow aspiration and biopsy when achieving CR/CMR based upon radiology. Immunohistochemistry (IHC) analyses should be performed under a microscope no matter bone marrow involves or not (Suggest detecting CD56、TIA-1、CD3、GrB、perforin, and EBER hybridization in situ, etc.).

6.5 PHARMACOKINETICS AND IMMUNOGENICITY

All subjects will receive pharmacokinetic and immunogenicity assessments Neutralizing antibody of CS1001 will be tested if the neutralizing antibody testing method is established.

Pharmacokinetics (PK): Blood samples will be collected within 60 minutes before infusion as pre-treatment samples at Cycle 1, 2, 3, 4, and 8, and within 30 minutes after infusion at Cycle 1 and 4 in the treatment phase. Blood samples for PK testing will be collected at the EOT visit, and safety follow-up visit at 30 days, and 90 days after the last dose of study treatment.

Immunogenicity: Pre-treatment blood samples are collected (within 60 minutes before dosing) at Cycle 1, 2, 3, 4, and every 4 cycles thereafter (e.g., Cycle 8, 12, 16, and so on). Blood samples for ADA testing will be collected at the EOT visit and safety follow-up visit at 30 days, and 90 days after the last dose of study treatment.

See Laboratory Manual for detailed instructions.

6.6 BIOMARKERS

The whole-exome sequencing of tumor tissue and immune repertoire test of peripheral monocytes will be performed if permitted by the Ethics Committee.

Whole exome sequencing of tumor tissue: seven (7) unstained FFPE tumor tissue slides should be collected at screening for whole-exome sequencing of tumor tissue; a total amount of 2 mL whole blood should be collected at screening as germline control of whole-exome sequencing.

If the tumor tissue and whole blood samples were not available at screening, retrospective collections of 7 archival FFPE tumor tissue slides and collection of 2 mL whole blood are allowed for whole-exome sequencing.

Subjects must provide tumor tissue and whole blood sample for biomarker analysis. However, if tumor tissue is not available or the subject is unwilling to participate in the biomarker study, the subject enrollment will be determined by the investigator in consultation with the sponsor's medical monitor.

7. REPORTING OF ADVERSE EVENTS

7.1 ADVERSE EVENTS

7.1.1 Definition of an Adverse Event

An AE is any untoward medical occurrence or any worsening of existing medical conditions after the subject signs the informed consent in a study, regardless of its relationship with the investigational treatment. An AE can, therefore, be any unfavorable and unintended sign, symptom, or disease temporally associated with the use of a medication, whether or not related to the medication. An AE can also be a pre- or post-treatment complication resulting from protocol-specified procedure, overdose, drug abuse/misuse, or occupational exposure. Any occurrence with a worsening or changing nature in the study or resulting from participation is also considered as an AE. All AEs should be recorded on the Adverse Events page on the subject's eCRF. All AEs are graded according to CTCAE v4.03.

The following conditions are not considered as AEs:

- Pre-existing or detected disease, condition, or laboratory finding before the screening visit that doesn't get worse during the study;
- Occurrence without any untoward medical event (for example elective operation, hospitalization due to social reason or for personal convenience);
- Any clinically significant medical occurrence or laboratory finding occurs before the subject signing the informed consent and is unrelated to any protocol-defined procedure. This is considered as a preexisting occurrence and should be recorded in the Medical History page on eCRF.

7.1.2 Adverse Event Monitoring

In the whole study course, AEs will be closely monitored before and after medication administration and reported by the medical staff. Subjects receive a general physical examination, hematology, urinalysis, hepatic and renal function and chemistry tests, and 12-lead ECG before and after the trial treatment. Vital signs will be monitored at various time points before and after investigational product administration on the dosing day.

7.1.3 Recording of Adverse Events

All AEs (including clinical symptoms, signs, or conditions) will be recorded in the eCRF, regardless of their relationship with the investigational treatment.

Time Period for Collection of Adverse Events

Adverse events will be collected from the time of signature of informed consent, throughout the treatment period and including the safety follow-up period of 90 days after the last dose of investigational product or the start of new anti-cancer treatment, whichever occurs earlier. After the safety follow-up visit (30 ± 3 days after the last investigational treatment), AEs can be collected by telephone follow-up 60 ± 3 days and 90 ± 3 days after the last dose. SAEs during the safety follow-up period will also be reported to the sponsor within a prespecified time frame.

For subjects with treatment discontinuation for any reason but still in the trial:

• Ongoing AEs should be followed up with data collection in the survival follow-up period

• Investigational product-related SAEs will still be collected during the survival follow-up period and reported to the sponsor according to the standard time frame and process of SAE reporting

All deaths after disease progression and during the survival follow-up period will be collected and recorded in the eCRF.

Refer to Table 7 for details.

	Treatment phase	Safety follow-up	Survival follow- up
Collection of all newly occurred AEs in eCRF	Yes	Yes	No
Collection of all ongoing AEs in eCRF	Yes	Yes	Yes
Collection of all drug-related SAEs in eCRF	Yes	Yes	Yes
Collection of all non-drug-related SAEs in eCRF	Yes	Yes	No

Table 7 Summary of Recording and Follow-up for Adverse Events and Deaths

Any AE that is unresolved at the subject's last visit in the study will be followed up by the investigator, but without further recording in the eCRF. The sponsor retains the right to request additional information for any subject with ongoing AE(s) at the end of the study if judged necessary.

If an investigator learns of any SAE, including death, at any time after the subject has been discontinued from the study, and he/she considers there is a reasonable possibility that the event is related to the investigational product, the investigator should notify the sponsor.

Variables

The following variables will be collected for each AE:

- Diagnosis/description of AE
- The date when the AE started and stopped
- Change of CTCAE grade
- Whether the AE is serious or not
- Investigator causality attribution against the investigational product (yes or no)
- Investigator causality attribution against the investigational product
- Outcome

In addition, additional variables including intervention will be collected for SAEs.

It is important to distinguish between serious and severe AEs. Severity is to describe the intensity, while the definition of SAEs is listed in Section 7.2.1. An AE of severe intensity need not necessarily be considered serious. For example, nausea that persists for several hours may be considered severe nausea, but not an SAE. On the other hand, a stroke that results in only a limited degree of disability may be considered a mile stroke but would be an SAE.

Events will be assessed and graded based upon the NCI CTCAE v4.03. For events of uncoded CTCAE grade, mild, moderate, and severe events will be converted to CTCAE level as recommended by the NCI CTCAE guideline. The latest version of CTCAE can be downloaded from the web of cancer treatment and evaluation plan (http://ctep.cancer.gov).

Causality Assessment

The investigator will assess the causal relationship between the investigational product and each event, and answer 'definitely related', 'possibly related', 'unlikely related', 'definitely unrelated' and 'not evaluable' to the question 'Do you consider that there is a possibility that the event may have been caused by the investigational product?'

Refer to Section 7.3.1 for the causality assessment guideline.

Adverse Events Based on Signs and Symptoms

All AEs spontaneously reported by subjects or caregivers and AEs found through observation will be recorded in the eCRFs. The subject's symptoms and signs will be recorded in the Diagnosis record (if possible) during the collection of AEs. If the diagnosis is confirmed, however, with symptoms and signs that are unlikely to be caused by the diagnosis should be recorded separately.

Adverse Events Based on Laboratory Tests and Examinations

All results of the protocol mandatorily required laboratory tests, vital sign measurements, ECG and other safety assessments will be summarized in the Clinical Study Report (CSR). If a parameter is worsened than the baseline level and meets the SAE criteria, or it leads to subject withdrawal apart from disease progression (see Disease Progression), it will be reported as an AE.

Worsened laboratory test results, vital signs, ECG, or other safety assessments with accompanying clinical symptoms and signs should be reported as supplementary information while the signs or symptoms reported as an AE. Reporting investigators should use clinical terminology whenever possible instead of laboratory terminology (for example anemia instead of low hemoglobin level). Non-mandatory test result that worsens with no accompanying clinical sign or symptom should be reported as an AE.

Worsening of laboratory test which is unequivocally due to disease progression will not be reported as an AE.

A newly found abnormal clinical test finding during physical examination or test results worse than the baseline level will be reported as an AE.

Disease Progression

Disease progression can be considered as deterioration of the subject's condition attributable to the disease under study. It may be an increase in the severity of the disease under study and/or increases in the symptoms of the disease. The development of new, or progression of existing metastasis to the primary tumor under study should be considered as disease progression and not an AE. Events, which are unequivocally due to disease progression, should not be reported as an AE during the study. Refer to Section 7.5.2 for a detailed explanation.

New Cancers

The development of new cancer should be regarded as an AE, and under most circumstances, they meet at least one criterion of SAE. New primary cancers are those that are not the primary reason for the administration of the investigational product and have been identified

after the subject's inclusion in this study. Metastasis of the primary tumor is not considered new cancer.

Deaths

All deaths that occur during the study, or within the protocol-defined follow-up period after the administration of the last dose of the investigational product, must be reported as follows:

- Death clearly the result of disease progression should be reported to the study monitor at the next monitoring visit and should be documented in the eCRF but should not be reported as an SAE.
- Where death is not clearly due to PD under study, the AE causing the death must be reported to the study monitor as an SAE within 24 hours. The report should contain a comment regarding the co-involvement of PD, if appropriate, and should assign main and contributory causes of death.
- Deaths with an unknown cause should always be reported as an SAE. Every effort should be made to identify the cause of death. An autopsy may be helpful in the assessment of the cause of death, and if performed a copy of the autopsy results should be forwarded to the representative of the sponsor in an expedited way within the predetermined timeframe.

7.2 SERIOUS ADVERSE EVENTS

7.2.1 Definition of A Serious Adverse Event

According to the definition from ICH (International Council for Harmonisation), SAE is any adverse medical event that meets any of the following criteria:

- Results in death;
- Is life-threatening (Note: life-threatening in the context of an SAE refers to a reaction in which the patient was at risk of death at the time of the reaction; it does not refer to a reaction that hypothetically might have caused death if more severe);
- Requires in subject hospitalization or prolongation of existing hospitalization (except for hospitalization due to medical insurance reimbursement issue or hospitalization without approval by the study doctor);
- Results in persistent or significant disability/incapacity;
- Is a congenital anomaly/birth defect;
- Other medically significant events.

These medically significant events that may not result in death, be life-threatening or require hospitalization may be considered serious when they jeopardize the participant and may require intervention to prevent one of the outcomes listed above. Medical and scientific judgment should be exercised in deciding whether the event should be reported in the light of expedited reporting rules. Examples of medically significant events include allergic bronchospasm requiring intensive treatment in an emergency room or at home, blood dyscrasias or convulsions that do not result in subject hospitalization, or the development of drug dependency or drug abuse. For the avoidance of doubt, infection resulting from drug deterioration is considered as a medically significant event and should be reported according to the expedited reporting rules.

The following hospitalizations that occur during the course of study should not be considered as SAEs:

- Admission into an emergency room, outpatient, or other departments for <24 hours and not hospitalized (unless is considered "medically significant event" or life-threatening event);
- Planned optional operation before ICF signing;
- Protocol-specified admission for medical/surgical treatment or monitoring;
- Admission for physical assessment;
- Admission for a Grade 1 AE, including overnight hospitalization due to nonmedical reasons after investigational product administration;
- Hospitalization for changing living conditions, which doesn't affect health conditions and doesn't involve medical/surgical intervention (for example for homeless, financial difficulty, family reasons, or management need).

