2. OBJECTIVES AND ENDPOINTS

Objectives	Endpoints
Primary objectives	Primary endpoints
To evaluate the efficacy of CS1001 in subjects with R/R ENKTL;	Objective response rate (ORR) assessed by IRRC according to Lugano 2014 classification
Secondary objectives	Secondary endpoints
To evaluate the efficacy of CS1001 in subjects with R/R ENKTL;	ORR assessed by investigators; CRR, PRR, TTR, DoR assessed by IRRC and investigators;
To evaluate the safety of CS1001 in subjects with R/R ENKTL	Severity and frequency of AEs, and frequency of SAEs
To evaluate the PK of CS1001	To determine the peak and trough serum concentration of CS1001
To evaluate the immunogenicity of CS1001	Number and percentage of subjects who develop ADA
Exploratory objectives	Exploratory endpoints
To evaluate the progression-free survival (PFS) and overall survival (OS) of R/R ENKTL subjects	6-months PFS rate, 6-month OS rate
To evaluate genetic aberrations in R/R ENKTL by whole-exome sequencing test of tumor tissues	The association between genetic aberrations and efficacy

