7.2.2 Serious Adverse Event Reporting

Any SAE occurring from the time of ICF signing to 90 days after the last dose of investigational product or the start of new anti-cancer therapy, whichever occurs earlier, must be reported to the designated representative of CRO or the sponsor **no later than 24 hours** when it gets learned of, regardless of causality with the investigational product. After the safety follow-up period, only treatment-related SAEs need to be recorded and reported.

Once an SAE occurs, the investigator should:

• Immediately take appropriate treatment measures for the subject and report to the sponsor as described above, and to drug regulatory authorities, health administrative authorities, and the Ethics Committee according to the local requirements.

Complete the SAE module in the EDC system, after which an automated email will be sent to the designated sponsor representative. In case EDC is down, all applicable modules of the sponsor's SAE form will be completed by the investigator/site staff. The investigator must assess the relationship of each SAE to each specific component of study treatment, complete and sign the SAE Report Form, and submit the completed form within 24 hours to the sponsor pharmacovigilance representative. Follow-up information is submitted in a new SAE report form and marked as the follow-up information of a previously reported SAE.

Any SAE that is unresolved at the end of study or subject withdrawal must be followed up until any of the following condition occurs:

- Event resolves; or
- Event stabilizes; or
- Event returns to baseline level (if baseline level available); or
- The event can be attributable to factors related with a medication other than the investigational product or unrelated with the investigator's behavior, or further information is unable to be obtained (when the subject or medical staff refuses to provide more information or when there's evidence showing the subject is lost to follow-up despite every effort made).

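### The serious adverse event (SAE) definition makes the hospitalization criterion depend on the study doctor's approval, so an unplanned admission elsewhere can lose SAE status and the SAE count can only fall.

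*Protocol*

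**What the plan says.** Protocol Section 7.2.1 introduces the definition with "According to the definition from ICH (International Council for Harmonisation), SAE is any adverse medical event that meets any of the following criteria" and lists the criteria. The one for in-patient admission or prolonged stay carries a parenthesis: "except for hospitalization due to medical insurance reimbursement issue or hospitalization without approval by the study doctor". Approval is not defined. There is no proviso for emergencies, for admission by another physician or hospital, or for endorsement by the study doctor afterwards.

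The last criterion, other medically significant events, is a matter of judgment: such events "may be considered serious when they jeopardize the participant and may require intervention to prevent one of the outcomes listed above".

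Section 7.2.2 attaches the expedited duty to SAEs. From consent to 90 days after the last dose or the start of new anti-cancer therapy, an SAE "must be reported to the designated representative of CRO or the sponsor" within 24 hours "when it gets learned of, regardless of causality with the investigational product". After that period only treatment-related SAEs are recorded and reported.

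Section 2 lists "Severity and frequency of AEs, and frequency of SAEs" as a secondary endpoint. The SAP's Adverse Events section plans a summary of serious treatment-emergent adverse events.

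**The concern.** Whether an event is serious should follow from what happened to the subject. Under this exemption, the same event with the same stay can be serious in one subject and not in another, depending only on whether the study doctor approved the admission.

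Admissions away from the site are foreseeable here. Dosing visits are three weeks apart. At days 60 and 90 after the last dose, a telephone call is an accepted alternative to the recommended full evaluation (Section 6.1.3.1). Survival contact is by telephone every 12 weeks (Section 6.1.3.3). Section 1.2.3 expects immune-related pneumonitis, colitis and hepatitis, and Appendix 13.4 itself anticipates hospital admission for the more severe forms of some of these.

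At stake are the 24-hour report and the SAE frequency. The trial has one arm, so no internal comparison would show a deficit.

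**Working it through.** No arithmetic applies: the plan gives no SAE or admission rate, so there is no figure to reproduce. The check sets the texts side by side and follows two otherwise identical events through them.

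**Step 1. What each text tests.**

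| Protocol text | What decides | Does approval matter? |
|---|---|---|
| 7.2.1, hospitalization criterion | Admission or prolonged stay, less insurance-driven stays, less unapproved stays | Yes |
| 7.2.1, list of admissions that are not SAEs | Reason for admission, length of stay under 24 hours without hospitalization, or Grade 1 event | No |
| 7.5.2.2, progression | Admission due only to the underlying malignancy | No |
| 7.3.2, severity assessment | Whether the event requires or prolongs hospitalization is recorded | No |

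Only the hospitalization criterion uses approval. The under-24-hour exclusion has a proviso that keeps medically significant and life-threatening events in; the approval exemption has none. Section 7.3.2 records hospitalization without the condition, so one subject's record can show that an event required admission and also that it was not serious.

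**Step 2. Two identical events.** Take the same reaction, grade and length of stay, neither fatal, life-threatening nor disabling.

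- Subject A is admitted with the study doctor's approval. The hospitalization criterion is met, so the event is an SAE.
- Subject B is admitted at a local hospital, and the study doctor hears of it later and has not approved it. Read literally, the criterion is not met. The event is an SAE only if someone judges it medically significant, and the wording there is permissive.

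**Step 3. What Subject B's event loses, by period** (Sections 7.1.3 with Table 7, 7.2.2 and 7.6).

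| Period | Classed as SAE | Not classed as SAE |
|---|---|---|
| Treatment and safety follow-up | 24-hour report; eCRF; counted in SAE frequency and serious treatment-emergent summary | eCRF entry as an adverse event; no 24-hour report unless it is a liver finding under 7.6; not in either SAE count |
| Survival follow-up, new and drug-related | Collected in the eCRF and reported | Table 7 does not collect newly occurring adverse events |

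In survival follow-up, SAE status alone decides whether Table 7 requires a record of a new drug-related event.

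**Step 4. Direction.** The exemption removes events from one criterion and adds none to any other. Its effect on the number of SAEs is therefore zero or negative.

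**Step 5. Is it cancelled elsewhere?** Protocol Sections 7.1.3, 7.2.2, 7.3.2 and 7.5.2 and the SAP safety section contain nothing that reverses or limits the exemption.

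**The case against.** The best case for the plan has four parts.

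**Intent and meaning of approval.** The clause sits beside insurance-driven admissions, which suggests that it is aimed at stays without medical need. Nothing says approval must come first, so a study doctor could endorse an emergency admission afterwards. This stands as a reason to write that status *can* be lost. It does not rescue the wording, which tests approval and leaves sites to choose a reading.

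**Other criteria remain.** Fatal, life-threatening and disabling events are still SAEs, and medically significant ones can be. This also stands. The gap is confined to events whose only seriousness criterion is hospitalization.

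**The data are not lost.** Section 7.1.3 states "All AEs (including clinical symptoms, signs, or conditions) will be recorded in the eCRF, regardless of their relationship with the investigational treatment", and Section 7.3.2 records hospitalization. Section 5.3.3 brings in the sponsor's medical monitor before permanent discontinuation for listed toxicities, Section 7.4 has the investigator alert the monitor to treatment-caused events, and Section 7.6 sends certain liver findings to the sponsor within 24 hours whether serious or not. The SAP also summarizes Grade 3 or higher and immune-related events and sponsor-assessed events of special interest. So a reader who infers that severe immune-related toxicity would vanish from the trial goes too far. These routes do not put the event into the SAE count, and only the liver rule has a 24-hour clock. Table 7's limit on new events in survival follow-up is untouched.

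**The clause may do useful work.** A reader might infer that, because the later list already covers non-medical admissions, this clause removes mainly genuine ones. The documents do not show that. The list does not clearly cover an admission at the subject's request for a Grade 2 or higher event that did not need a bed. That is a reason to allow a replacement based on medical need as well as plain deletion.

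**Conclusion.** The exemption is current, operative text, and it makes SAE status depend on something other than the event. An unplanned admission outside the study site, with hospitalization as its only seriousness criterion, can be missed as an SAE. It can then miss the 24-hour report and both SAE summaries and, if new and drug-related in survival follow-up, have no record required by Table 7. Any bias is towards fewer SAEs. The primary endpoint, response rate by independent review, is not affected.

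Two stronger readings are tempting and unsupported. One is that such admissions *are* not SAEs and *are* under-reported: approval is undefined and may be given later, and the other criteria still apply. The other is a numerical shortfall. If 20-30% of 80 subjects (16 to 24) had an SAE by hospitalization alone and 25-50% of those admissions were elsewhere, then 16 × 0.25 = 4 to 24 × 0.50 = 12 subjects, or 5 to 15 percentage points, would be at risk. Both percentages are guesses with no source in the documents, and the sum assumes that every such admission loses its status. It should not be used as an estimate.

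The conclusion rests on a literal reading of the parenthesis. It does not rest on the wording of the ICH definition, which the protocol cites but does not reproduce.

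**What to change.** In Protocol Section 7.2.1, delete the second half of the parenthesis, on the study doctor's approval. Alternatively, replace it with an exemption for admissions where there was no adverse event or no medical need. Keep the insurance exemption and the existing list of admissions that are not SAEs. Check the result against the ICH source that the section names, and make it consistent with Section 7.3.2, which records hospitalization without an approval condition.

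Before safety database lock, query sites for admissions screened out under the clause and reclassify those that qualify. A listing of adverse events recorded as requiring or prolonging hospitalization but not marked serious would find candidates from treatment and safety follow-up. For survival follow-up, sites must be asked directly, because Table 7 does not collect new events there.

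The cost is one clause in an amendment or clarification letter and one round of queries. The downside is somewhat more 24-hour reports and a slightly higher reported SAE frequency.
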